9.4.1.3. Treatment Guidelines and Dose Modifications for Specific Adverse Events

Adverse events of special interest, which may or may not be associated with necitumumab and/or pembrolizumab therapy, include hypersensitivity/IRR, skin reactions, conjunctivitis, electrolyte abnormalities, pneumonia and sepsis, pneumonitis, diarrhea/colitis, type 1 diabetes mellitus, hypophysitis, hyper- or hypothyroidism, liver injury, renal failure/nephritis, and thromboembolic events.

9.4.1.3.1. Hypersensitivity and Infusion-Related Reactions

Refer to the NCI-CTCAE Version 4.0 for grading for hypersensitivity and IRRs.

Consistent with usual medical practice, selected parenteral medications may be utilized as detailed below. Additional treatments, chosen according to clinical symptoms and local standards, may be utilized at investigator discretion.

9.4.1.3.1.1. Management of Infusion Reactions for Necitumumab

Hypersensitivity and IRRs were reported with necitumumab. The onset of events usually occurred after the first or second administration of necitumumab. Monitor patients during and following the infusion for signs of hypersensitivity and IRRs with resuscitation equipment readily available.

[Table JFCQ.9.4](#) provides general treatment recommendations for hypersensitivity/IRRs to necitumumab.

Table JFCQ.9.4. Necitumumab Infusion-Related Reaction Treatment Guidelines

Grade of Reaction	Management Recommendations	
	First Occurrence	Second Occurrence
1	
 Decrease infusion rate by 50% for the duration of the infusion, and monitor patient for worsening of condition.^a For all subsequent infusions, premedicate with diphenhydramine hydrochloride 50 mg I.V. (or equivalent); additional premedication may be administered at the investigator's discretion. 	
 Decrease infusion rate by 50% for the duration of the infusion, and monitor patient for worsening of condition.^a Administer dexamethasone 10 mg I.V. (or equivalent). For all subsequent infusions, premedicate with diphenhydramine hydrochloride 50 mg I.V. (or equivalent), acetaminophen 650 mg orally (or equivalent), and dexamethasone 10 mg I.V. (or equivalent); additional premedication may be administered at the investigator's discretion.
2	
 Stop the infusion, and resume the infusion when the infusion reaction has resolved to ≤ Grade 1; decrease infusion rate by 50% when the infusion resumes.^a Monitor patient for worsening of condition. If necessary, administer diphenhydramine hydrochloride 50 mg I.V. (or equivalent), acetaminophen 650 mg orally for fever, and oxygen. For all subsequent infusions, premedicate with diphenhydramine hydrochloride 50 mg I.V. (or equivalent); additional premedication may be administered at the investigator's discretion. 	
 Stop the infusion, and resume the infusion when the infusion reaction has resolved to ≤ Grade 1; decrease infusion rate by 50% when the infusion resumes.^a Administer dexamethasone 10 mg I.V. (or equivalent). Monitor patient for worsening of condition. If necessary, administer diphenhydramine hydrochloride 50 mg I.V. (or equivalent), acetaminophen 650 mg orally for fever, and oxygen. For all subsequent infusions, premedicate with diphenhydramine hydrochloride 50 mg I.V. (or equivalent), acetaminophen 650 mg orally (or equivalent), and dexamethasone 10 mg I.V. (or equivalent); additional premedication may be administered at the investigator's discretion.
3-4	
 Stop the infusion and disconnect the infusion tubing from the patient. Administer diphenhydramine hydrochloride 50 mg I.V. (or equivalent), dexamethasone 10 mg I.V. (or equivalent), bronchodilators for bronchospasm, epinephrine, and other medications / treatments as medically indicated. Hospital admission may be indicated. Permanently discontinue necitumumab. 	N/A

Abbreviations: IRRs = infusion-related reactions; I.V. = intravenously; N/A = not applicable.

^a Once the infusion rate has been reduced for a Grade 1 or 2 hypersensitivity/IRRs, it is recommended that the lower infusion rate be utilized for all subsequent infusions. The infusion duration should not exceed 2 hours.

9.4.1.3.1.2. Management of Infusion Reactions for Pembrolizumab

Signs and symptoms usually develop during or shortly after drug infusion and generally resolve completely within 24 hours of completion of infusion.

Table JFCQ.9.5 shows treatment guidelines for patients who experience an infusion reaction associated with administration of pembrolizumab (MK-3475).

Table JFCQ.9.5. Pembrolizumab Infusion-Related Reaction Treatment Guidelines

NCI CTCAE Grade	Treatment	Premedication at Subsequent Dosing
Grade 1	Increase monitoring of vital signs as medically indicated until the patient is deemed medically stable in the opinion of the investigator.	None
Grade 2	
Stop Infusion and monitor symptoms. Additional appropriate medical therapy may include but is not limited to:
 
 I.V. fluids Antihistamines NSAIDS Acetaminophen Narcotics 
Increase monitoring of vital signs as medically indicated until the patient is deemed medically stable in the opinion of the investigator.
 
If symptoms resolve within one hour of stopping drug infusion, the infusion may be restarted at 50% of the original infusion rate (e.g., from 100 mL/hr to 50 mL/hr). Otherwise, dosing will be held until symptoms resolve and the patient should be premedicated for the next scheduled dose.
 
Patients who develop Grade 2 toxicity despite adequate premedication should be permanently discontinued from further trial treatment administration.
	
Patient may be premedicated 1.5 hr (\pm 30 minutes) prior to infusion of pembrolizumab (MK-3475) with:
 
Diphenhydramine 50 mg po (or equivalent dose of antihistamine).
 
Acetaminophen 500-1000 mg po (or equivalent dose of antipyretic).

Grades 3 or 4	
Stop Infusion. Additional appropriate medical therapy may include but is not limited to:
 
 I.V. fluids Antihistamines NSAIDS Acetaminophen Narcotics Oxygen Pressors Corticosteroids Epinephrine 
Increase monitoring of vital signs as medically indicated until the patient is deemed medically stable in the opinion of the investigator.
 
Hospitalization may be indicated.
 
Patient is permanently discontinued from further trial treatment administration.
	No subsequent dosing

Appropriate resuscitation equipment should be available in the room and a physician readily available during the period of drug administration.

Abbreviations: I.V. = intravenous; NCI CTCAE = National Cancer Institute Common Terminology Criteria for Adverse Events; NSAIDs = non-steroidal anti-inflammatory drugs; po = oral.

If a patient should have a hypersensitivity/IRR to necitumumab or pembrolizumab, all attempts should be made to obtain an anti-necitumumab antibody and PK blood samples for necitumumab as close to the onset of the event as possible, at the resolution of the event, and 30 days following

the event. The procedure for sample collection and handling is described in a separate procedural manual.

9.4.1.3.2. Skin Reactions

9.4.1.3.2.1. Reactive Treatment

Reactive treatment recommendations for skin reaction, based on the Canadian recommendations presented by Melosky et al. (2009), are summarized in [Table JFCQ.9.6](#).

Skin rash (any grade) should be treated as per [Table JFCQ.9.6](#). If a patient experiences a Grade 1 or 2 acne-like rash, necitumumab treatment should continue without dose modification or delay. Dose delays and or modifications for necitumumab are to be considered in case of skin reactions of Grade 3 or that are considered intolerable. If a patient experiences Grade 4 skin reactions, treatment with necitumumab should be permanently discontinued.

Table JFCQ.9.6. Managing Skin Reactions

Grade of Reaction	Recommendations for Management
1	
 Administer topical clindamycin 2% and topical hydrocortisone 1% in lotion base twice daily to affected areas until resolution of reaction. Patients are advised to take appropriate protective measures prior to sun exposure to avoid exacerbation of rash severity.
2	
 Administer topical clindamycin 2% and topical hydrocortisone 1% in lotion base twice daily to affected areas until resolution of reaction. If clinically appropriate in the opinion of the investigator, administer oral minocycline or doxycycline 100 mg twice daily (or equivalent), for a minimum of 4 weeks and continuing for as long as rash is symptomatic. Patients are advised to take appropriate protective measures prior to sun exposure to avoid exacerbation of rash severity.
3	
 Administer topical clindamycin 2% and topical hydrocortisone 1% in lotion base twice daily to affected areas until resolution of reaction. Administer oral minocycline or doxycycline 100 mg twice daily (or equivalent), for a minimum of 4 weeks and continuing for as long as rash is symptomatic. Patients are advised to take appropriate protective measures prior to sun exposure to avoid exacerbation of rash severity. Necitumumab administration will be temporarily withheld until symptoms resolve to Grade ≤ 2, but not for longer than a maximum of 6 weeks following Day 1 of the most recent treatment cycle. Following improvement to Grade ≤ 2, necitumumab may be re-administered, with a dose reduction of 50% but not below 400 mg. This dose may be increased to 75% of the original dose) after a minimum of 1 treatment cycle (3 weeks), if symptoms do not recur. If symptoms do not recur for another treatment cycle, the dose may be re-escalated to the initial dose). If reactions do not resolve to Grade ≤ 2 after 6 weeks (that is, after withholding 2 consecutive doses of necitumumab), or if reactions recur or become intolerable at 50% of the original dose, necitumumab treatment should be permanently discontinued. Patients who experience Grade 3 skin induration / fibrosis will be immediately discontinued from necitumumab.
4	
 Administer topical clindamycin 2% and topical hydrocortisone 1% in lotion base twice daily to affected areas until resolution of reaction. Administer oral minocycline or doxycycline 100 mg twice daily (or equivalent), for a minimum of 4 weeks and continuing for as long as rash is symptomatic. Patients are advised to take appropriate protective measures prior to sun exposure to avoid exacerbation of rash severity. Necitumumab administration must be immediately and permanently discontinued.

If necitumumab therapy is delayed due to acneiform rash, pembrolizumab may be administered without interruption in the absence of disease progression.

A dermatology referral may be indicated for skin reactions that do not improve following 1-2 weeks of treatment, reactions that are severely symptomatic (for example, necrosis, blistering, or petechial or purpuric lesions), reactions of NCI-CTCAE Grade ≥ 3 , or reactions with an uncharacteristic appearance.

As with all concomitant medications/procedures, any actions taken to ameliorate skin toxicity will be documented in the concomitant medication module of the electronic CRF (eCRF).

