- The patient has an evaluable tumor tissue, an archived formaldehyde fixed-paraffin embedded (FFPE) block or at a minimum 15 slides (freshly cut slides should be submitted to the central laboratory), is available for biomarker analyses, or if not available, patient is willing to undergo a tumor biopsy of an extra-central nervous system lesion (core or excisional biopsy).
- The patient has resolution to Common Terminology Criteria for Adverse Events (CTCAE) Grade ≤ 1 of all clinically significant toxic effects of prior chemotherapy, surgery, or radiotherapy (with the exception of alopecia).
- Eastern Cooperative Oncology Group performance status (ECOG PS) score of 0-1.
- The patient has no brain metastases that are symptomatic.

Test Product, Dosage, and Mode of Administration:

- Necitumumab is a sterile, preservative-free, intravenous infusion supplied in 50-mL vials containing 16 mg/mL (800 mg/50 mL) of product, and administered over 60 minutes at a dose of 600 mg or 800 mg on Days 1 and 8 of each 21-day cycle.
- Pembrolizumab drug product is available in 2 dosage forms intended for intravenous administration: a lyophilized powder, 50 mg/vial, ready to be reconstituted with sterile water for injection prior to use, and a liquid, 100 mg/vial, both in Type I glass vials intended for single use only. Pembrolizumab is administered over 30 minutes (-5 min/+ 10 min) at a dose of 200 mg on Day 1 of each 21-day cycle.

Reference Therapy, Dose, and Mode of Administration: Not Applicable

Planned Duration of Treatment: Baseline period: up to 21 days Treatment period: 21 days treatment cycle Short-term follow-up (postdiscontinuation): 30 days Long-term follow-up (postdiscontinuation): begins the day after short-term follow-up is completed and continues until the patient's death or overall study completion Study completion: Part A and Part B of this study will be considered complete approximately 6 months after the last patient in Part B has been enrolled, and Part C of this study will be considered complete approximately after all the patients in Part C have completed 8 cycles or discontinued early. Continued Access Period: Patients who are on study therapy at study completion may continue to receive study therapy in the continued access period until they meet the discontinuation criteria.

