7.3.2. Discontinuation of Study Therapy

Patients will be discontinued from the study treatment in the following circumstances:

- Enrollment in any other clinical trial involving a study drug or enrollment in any other type of medical research judged not to be scientifically or medically compatible with this study.
- The patient, for any reason, requires treatment with another therapeutic agent that has been demonstrated to be effective for treatment of the study indication; discontinuation from study therapy occurs prior to introduction of the new agent.
- Investigator/Physician Decision
 - The investigator/physician decides that the patient should be withdrawn from the study due to an intercurrent illness or change in the patient's condition that renders the patient unsuitable for further treatment in the opinion of the investigator.

- Any study therapy-related event that is deemed life-threatening, regardless of grade, warrants discontinuation of that therapy and/or discontinuation from all therapy if appropriate in the opinion of the investigator.
- If the patient has progressive disease (PD, confirmed by irRECIST or unconfirmed but with clinically worsening/deterioration [Section 10.1.5.1 and Table JFCQ.10.1]).
- Any event(s) which would require a given study therapy to be modified by more than 2 dose reductions or to be held for more than 6 weeks following Day 1 of the most recent cycle warrants discontinuation of that therapy.
- The patient becomes pregnant during treatment.
- Patient Decision
 - The patient or patient's designee (for example, parents or legal guardian) requests to be withdrawn from the study or study treatment.
- Sponsor Decision
 - The sponsor stops the study or stops the patient's participation in the study for medical, safety, regulatory, or other reasons consistent with applicable laws, regulations, and good clinical practices (GCP).
- The patient is significantly noncompliant with study procedures and/or treatment.
- An unacceptable AE/toxicity (for example, a persistent moderate toxicity that is intolerable to the patient).
- A Grade 3 to 4 IRR, and potentially other drug-related AEs, as specified in Section 9.4.1 below.

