9.4. Selection and Timing of Doses

The first treatment will be administered within 7 days of enrollment. Study treatment will be administered as described in Section 9.1.

A cycle is defined as an interval of 21 days.

Administration of pembrolizumab Day 1 dose, followed by necitumumab will trigger the start of a new cycle. Infusions administered within 3 days before or after the planned infusion time point due to holidays, weekends, bad weather, or other unforeseen circumstances will be permitted and not counted as a protocol deviation. The necitumumab Day 8 dose can be delayed up to 5 days. Beyond that, the Day 8 dose will have to be omitted in order to maintain the 21 day cycle. **A minimum of 7 days' interval between any necitumumab doses must be maintained.**

A patient may continue to receive study treatment until he or she meets 1 or more of the specified reasons for discontinuation (as described in Section 7.3), or complete remission is diagnosed (as described in Section 8.1).

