9.4.1.2.2. Necitumumab

Prior to each administration of necitumumab, all toxicities associated with necitumumab must have resolved to Grade ≤ 2 (except for alopecia and skin toxicity) or baseline. Pretreatment laboratory data may not be older than 72 hours (Day 1 of each cycle) or 24 hours (Day 8 of each cycle).

If the criteria are not met at the time of a planned treatment, the following general rules for the management of treatment delays apply:

- In the case of reversible Grade 3-4 necitumumab-related toxicity (for example, fatigue, anorexia, and fever), administration of necitumumab will be at the reduced dose (refer to [Section 9.4.1.2.2.1](#)) or interrupted, but pembrolizumab will continue according to the planned schedule.
- If administration of necitumumab is delayed for more than 6 weeks (2 cycles) after Day 1 of the most recent treatment cycle, the patient should be discontinued from necitumumab treatment.

9.4.1.2.2.1. Necitumumab Dose Modifications

The following are general dose-modification guidelines for toxicity associated with necitumumab. Please see [Section 9.4.1.3](#) for specific information on the management of necitumumab-related hypersensitivity/IRRs, skin reactions, conjunctivitis, and hypomagnesemia.

For patients starting Cycle 1 in Part A and possible Part B of the study at necitumumab 600 mg on Days 1 and 8, one dose reduction is permitted. Patients who cannot tolerate necitumumab 400 mg should discontinue necitumumab; such patients may continue with pembrolizumab as a single agent.

For patients starting Cycle 1 at dose level 800 mg on Days 1 and 8 in Part A and possible Part B and Part C of the study, 2 dose reductions are allowed following reversible CTCAE Grade ≥ 3 AEs that require delay of necitumumab treatment for up to 6 weeks following Day 1 of the most recent treatment cycle, unless DLT criteria are met (Cycle 1 Parts A and C). In this setting, necitumumab may be re-administered at a reduced dose (600 mg) if necessary only if AE is resolved to Grade ≤ 2 . A second dose reduction is permitted for this level of event (Grade ≥ 3). Necitumumab must be discontinued if further dose reduction is required beyond 400 mg on Days 1 and 8 Q3W. The patient may continue to receive pembrolizumab as a single agent.

Necitumumab dose adjustments are allowed both within a cycle and between cycles.

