Necitumumab may be held up to 6 weeks (2 cycles) to permit sufficient time for recovery from the toxicity. If a dose delay occurs, the investigator may resume necitumumab dosing at the same dose level for the remainder of the study or at reduced dose (assuming resolution to at least Grade 1 for nonhematologic and at least Grade 2 for hematologic toxicity). If the patient experiences the same toxicity with the same or greater severity (CTCAE grade) requiring a dose delay within a cycle or at start of the next cycle, the patient must be dose reduced and not re-challenged a second time at the prior dose level.

If a patient experiences CTCAE Grade ≥ 3 hematologic toxicity possibly related to necitumumab, unless DLT criteria are met, then dosing must be delayed (until the toxicity resolves to either baseline or at least Grade 2) and the dose of necitumumab must be reduced by 1 dose level (see below).

If a patient experiences CTCAE Grade ≥ 3 nonhematologic toxicity possibly related to necitumumab, unless DLT criteria are met, then dosing must be delayed (until the toxicity resolves to either baseline or at least Grade 1) and the dose of necitumumab must be reduced by 1 dose level (see below).

For patients requiring dose reduction(s), any re-escalation to a prior dose level is permitted only after consultation with the Lilly CRP. After re-escalation, subsequent dose adjustments should be based on the dose of necitumumab that the patient is currently receiving. Following a dose reduction, the dose of necitumumab may be re-escalated to the pre-reduction dose, provided that at least 2 administrations of the reduced dose were given, and only after consultation with the Lilly CRP.

Table JFCQ.9.3. Dose Adjustments of Necitumumab

Dose Adjustment Level	I.V. Dose	Frequency
0	800 mg	Days 1 and 8 Q3W
-1	600 mg	Days 1 and 8 Q3W
-2	400 mg	Days 1 and 8 Q3W

Abbreviations: I.V. = intravenous; Q3W = every 3 weeks.

Events that necessitate more than 2 dose reductions warrant discontinuation from necitumumab treatment. For dose modifications in response to specific AEs related to necitumumab, please see Section [9.4.1.3](#).

Patients who enter the study with symptoms or laboratory values equivalent to NCI-CTCAE Version 4.0 Grade 1-2 AEs should not have dose reductions related to the persistence or mild worsening (for example, from Grade 1 to Grade 2) of those symptoms or laboratory values.

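### The Grade 3 skin-reaction stop rule equates 6 weeks with two withheld necitumumab doses, but three are withheld when onset comes before the Day 8 dose

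*Protocol*

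**What the plan says.** The Grade 3 row of Table JFCQ.9.6 (Protocol 9.4.1.3.2.1) states its time limit twice. It first withholds necitumumab until the reaction is Grade 2 or lower, "but not for longer than a maximum of 6 weeks following Day 1 of the most recent treatment cycle". It then requires permanent discontinuation if that improvement has not occurred "after 6 weeks (that is, after withholding 2 consecutive doses of necitumumab"). The dose count carries no condition on when in the cycle the reaction began.

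The Synopsis gives the schedule: necitumumab is administered "at a dose of 600 mg or 800 mg on Days 1 and 8 of each 21-day cycle".

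The same 6-week limit appears in three other places, none of which counts doses:
- Section 7.3.2 covers any event that requires a study therapy "to be held for more than 6 weeks following Day 1 of the most recent cycle warrants discontinuation of that therapy".
- Section 9.4.1.2.2 stops necitumumab under this condition: "If administration of necitumumab is delayed for more than 6 weeks (2 cycles) after Day 1 of the most recent treatment cycle".
- Section 9.4.1.2.2.1 says: "Necitumumab may be held up to 6 weeks (2 cycles) to permit sufficient time for recovery from the toxicity".

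**The concern.** The parenthetical presents two withheld doses as another way of saying six weeks. With two doses in every three-week cycle, the six weeks from Day 1 of a cycle contain four planned doses. The number withheld therefore depends on how many had been given before the reaction started. The equivalence can hold for one onset time and fail for another.

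This matters because the sentence governs permanent discontinuation. Two sites could follow the row in good faith and reach different decisions, one counting weeks and the other counting doses. The practical effect would fall on necitumumab exposure and discontinuation in individual patients.

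**Working it through.** **Inputs**
- Dosing on Days 1 and 8 of a 21-day cycle (Synopsis; Section 9.4). Counted from Day 1 of the last cycle started, planned days are 1, 8, 1 + 21 = 22, 8 + 21 = 29, and 1 + 42 = 43.
- Limit: 6 weeks after Day 1 (Grade 3 row), so 1 + 42 = Day 43.
- Start of a cycle (Section 9.4): "Administration of pembrolizumab Day 1 dose, followed by necitumumab will trigger the start of a new cycle". On this reading, a Day 1 on which necitumumab is withheld does not restart the clock.

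**Count:** planned doses after onset and before Day 43.

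| Onset | Doses withheld before Day 43 | Number | Stated in the row |
|---|---|---|---|
| After the Day 8 dose | Days 22, 29 | 2 | 2 |
| Between the Day 1 and Day 8 doses | Days 8, 22, 29 | 3 | 2 |

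The plan's figure is reproduced for the later onset, where the next dose would fall on Day 43 itself. It is not reproduced for the earlier onset.

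**Size of the gap for the earlier onset**
- Stop at the second missed dose: Day 22, and 43 − 22 = 21 days before the limit.
- Stop when the next dose falls due after two misses: Day 29, and 43 − 29 = 14 days before the limit.
- Recovery time from the first missed dose: 43 − 8 = 35 days under the 6-week limit, against 22 − 8 = 14 or 29 − 8 = 21 days under the dose count.

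**Comparison with the row's own treatment.** The row asks for at least 4 weeks of oral minocycline or doxycycline. If that starts at onset on Days 2 to 7, four weeks are complete on Days 2 + 28 = 30 to 7 + 28 = 35. Both dose-count stop dates come before this; Day 43 does not.

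**Does any allowed flexibility rescue the count of two?**
- Day 8 delay. Section 9.4 says: "The necitumumab Day 8 dose can be delayed up to 5 days", and a dose not given by then is omitted. If it is given by 8 + 5 = Day 13, the later-onset case applies. If it is omitted, it is a missed dose and the count is 3.
- The 3-day infusion window moves individual days but does not bring 3 down to 2.
- Counting the Day 43 dose, which falls on the limit, gives 4 (earlier onset) and 3 (later onset).
- Six weeks measured from the first withheld dose gives 4 in both cases: Days 8, 22, 29, 43, or Days 22, 29, 43, 50.
- Moving the anchor to Day 22 puts the limit at 22 + 42 = Day 64 and gives 5 (Days 8, 22, 29, 43, 50) and 4 (Days 22, 29, 43, 50).

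No variant gives two for the earlier onset.

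**The case against.** The strongest reply is that the operative condition is the 6 weeks and the parenthetical only explains it. On Day 22 or Day 29 six weeks have not passed. A site stopping then would let the explanation override both the stated period and the limit given earlier in the same row, which three other sections repeat. The explanation is also correct for the later onset, and the error leans towards stopping early in a patient whose toxicity has not resolved. This stands, and it is why the consequence is small. It does not make the count right, and a rule for permanent discontinuation should not offer two stop dates.

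A second reply concerns the anchor. Pembrolizumab continues on schedule during a necitumumab hold, so a pembrolizumab-only Day 1 might be taken to start a new cycle and move the limit. This does not help. If every such Day 1 restarted the clock, one would come every 3 weeks and the 6-week limit could never be reached while pembrolizumab stayed on schedule. A single move to Day 22 makes the dose count wrong for both onsets. It is fair to say that the 14- and 21-day figures depend on the anchor used here.

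**Conclusion.** The concern holds, as a minor wording error in an operative rule. For a Grade 3 reaction starting between the Day 1 and Day 8 doses, the 6-week limit corresponds to three withheld doses. The figures assume planned dosing days and a clock that runs from the last Day 1 on which both drugs were given. The early stop also requires a site to follow the dose count instead of the stated weeks.

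The row is likely to be used. Section 5.2 reports Grade 3 or higher skin reactions in 8.2% of the necitumumab arm of SQUIRE, and Grade 3 or higher skin or subcutaneous disorders in 14.1% of the necitumumab arm of INSPIRE, both in combination with chemotherapy. Those rates do not show how many reactions start in the first week of a cycle and persist, so no patient count can be given.

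**What to change.** In the Grade 3 row of Table JFCQ.9.6, delete the parenthetical about two doses, or replace it with (2 cycles) to match Sections 9.4.1.2.2 and 9.4.1.2.2.1. Keep six weeks counted from Day 1 of the latest cycle as the only limit. The cost is one parenthetical in one table row, in a protocol amendment. The design, analyses and sample size do not change.
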